SAP Version 1 was created and approved prior to first patient visit and any unblinding of the study team.

2. Study Objectives

2.1. Primary Objective

[Table 1](#) shows the primary objectives and endpoints used to determine the safety and efficacy of AstroStem in patients with Alzheimer's disease.

Table 1. Primary Objectives and Endpoints

Objectives	Endpoints

Primary Efficacy
 
• To evaluate the efficacy of AstroStem in patients with Alzheimer's disease 
Primary Safety
 
• To evaluate the safety of AstroStem in patients with Alzheimer's disease	
• Change of ADAS-Cog (Alzheimer's Disease Assessment Scale-cognitive subscale) from baseline (Visit 3) to Visit 13 (Week 30)• Number of subjects with treatment related adverse events as assessed by analysis of adverse events including symptoms, and abnormal findings on physical examination, vital signs, ECG, and standard laboratory examination results

2.2. Secondary Objectives

[Table 2](#) shows the secondary objectives and endpoints used to determine the safety and efficacy of AstroStem.

Table 2. Secondary Objectives and Endpoints

Objectives	Endpoints

Secondary Efficacy
 
• To evaluate the efficacy of AstroStem in patients with Alzheimer's disease	
• Change of MMSE (Mini-mental status examination) from baseline at Week 30 (Visit 13)• Changes of CDR-SOB (Clinical Dementia Rating-Sum of Boxes) from baseline at Week 30

	
Changes of NPI (Neuropsychiatric Inventory) from baseline at Week 30Changes of GDS (Geriatric Depression Scale) from baseline at Week 30Change of ADCS-ADL (Alzheimer's Disease Cooperative Study Activities of Daily Living) from baseline at Week 30 
Secondary Safety
 
To evaluate the safety of AstroStem in patients with Alzheimer's disease
--	--

2.3. Exploratory Objectives

[Table 3](#) shows the exploratory objectives and endpoints used to determine the safety and efficacy of AstroStem.

Table 3. Exploratory Objectives and Endpoints

Objectives	Endpoints
Exploratory Efficacy 
To evaluate the efficacy of AstroStem in patients with Alzheimer's disease	
Change of ADAS-Cog from baseline at Visit 6, 9, 12 and 14 or Early TerminationChange of MMSE from baseline at Visit 6, 9, 12 and 14 or Early TerminationChanges of CDR-SOB from baseline at Visit 6, 9, 12 and 14 or Early TerminationChanges of NPI from baseline at Visit 6, 9, 12 and 14 or Early TerminationChanges of GDS from baseline at Visit 6, 9, 12 and 14 or Early TerminationChange of ADCS-ADL from baseline at Visit 6, 9, 12 and 14 or Early TerminationSummary of Biomarkers in blood: Amyloid beta 40, Amyloid beta 42, Amyloid precursor protein intracellular domain (AICD), soluble neuregulin-1 (sNRG-1) at baseline, Visit 13 and 14 or Early Termination
Exploratory Safety 
To evaluate the efficacy of AstroStem in patients with Alzheimer's disease	
Changes of C-SSRS from baseline at Visit 6, 9, 12 and 14 or Early TerminationChange of MRI imaging results from baseline at Visit 9 and 14 or Early Termination

3. Study Design

3.1. Summary of Study Design

This is a randomized, double-blind, placebo-controlled study to evaluate the efficacy and safety of AstroStem for the treatment of Alzheimer's Disease. Three investigational centers in the United States may be utilized so that a total of approximately 22 subjects will be randomized. At Week -4, 30 mL of abdominal adipose tissue will be taken by liposuction from subjects. The adipose tissue samples will be sent to Biostar Stem Cell Research Institute to isolate AdMSCs. The isolated AdMSCs or saline will be sent to the clinical sites with identical syringes to preserve double-blinding of the study. A total 2×10^8 AdMSCs in 220 mL of saline or the same volume of saline will be administered via I.V. at Week 0. This procedure will be repeated 9 times at 2-week interval. Subjects will be scheduled for two follow-up visits at Weeks 30 and 52 to evaluate primary and secondary outcome endpoints. The schedule of Assessments is illustrated in [Table 4](#).

Table 4. Schedule of Assessments

Procedure	Screen		Treatment											Follow-up		Early Termination
	V1	V2	V3	V4	V5	V6	V7	V8	V9	V10	V11	V12	V13	V14		
Tested Group	-W8	-W4	W0	W2	W4	W6	W8	W10	W12	W14	W16	W18	W30	W52		
Informed Consent ¹	V															
Inclusion/Exclusion Criteria	V															
Demographic information	V															
Medical/medication history	V															
Physical examination	V		V		V			V			V	V	V	V		
Vital signs	V	V	V	V	V	V	V	V	V	V	V	V	V	V		
Hematology, serum chemistry, and urinalysis ²	V		V		V			V			V	V	V	V		
Pregnancy test ³	V		V								V	V	V	V		
Electrocardiogram	V		V		V			V			V	V	V	V		
Chest X-ray	V															
Liposuction		V														
Serum for IP		V	V		V		V		V							
ADAS-Cog			V		V			V			V	V	V	V		
MMSE	V		V		V			V			V	V	V	V		
CDR-SOB			V		V			V			V	V	V	V		
NPI			V		V			V			V	V	V	V		
GDS			V		V			V			V	V	V	V		
C-SSRS			V		V			V			V	V	V	V		
ADCS-ADL			V		V			V			V	V	V	V		
MRI Scan	V							V				V	V	V		

Biomarker ⁴			V									V	V	V
Drug administration			V	V	V	V	V	V	V	V	V			
Concomitant medications		V	V	V	V	V	V	V	V	V	V	V	V	V
Adverse events		V	V	V	V	V	V	V	V	V	V	V	V	V

¹ Informed Consent Form should be signed prior to any clinical trial related activities

² See Appendix 1 for the complete list of laboratory tests

³ Serum pregnancy test is performed for all females of childbearing potential.

⁴ Amyloid beta 40, Amyloid beta 42, Amyloid precursor protein intracellular domain (AICD), soluble neuregulin-1 (sNRG-1)

3.2. Determination of Sample Size

There was no formal sample size calculation since this is a phase 1/2 study and is not a hypothesis-driven study. The number of enrolled subjects is predefined approximately at n=22, about 11 subjects per group

3.3. Method of Assignment to Treatment

Patients who meet all criteria for enrollment will be randomized to double-blind treatment at visit 2. Assignment to treatment group will be determined by a computer-generated randomization code using the electronic data capture (EDC) system on Visit 2 (Week -4).

Blinding of the drug contents from the subjects, investigators, and other study personnel at each clinical site is necessary. Because two syringes of AstroStem and control are different, one physician must be only assigned to the role of syringe injection in order to maintain the double-blinding against other site physicians and staffs.

4. Statistical Methods

4.1. General Considerations

This document describes the statistical analyses planned prior to final treatment assignment unblinding of the aggregate database. Any change to the data analysis methods described in the protocol will require an amendment ONLY if it changes a principal feature of the protocol. Any other change to the data analysis methods described in the protocol and the justification for making the change will be described in the clinical study report (CSR). Additional exploratory analyses of the data will be conducted as deemed appropriate.

All tests of treatment effects will be conducted at a two-sided alpha level of 0.05 unless

otherwise stated, and all confidence intervals (CI's) will be given at a two-sided 95% level, unless otherwise stated. Statistical analysis will be performed using SAS software (SAS, Version 9.1.2 or higher).

The following general terms will be used globally in the SAP:

- Unless otherwise specified, the statistical analyses will be reported using summary tables and data listings.
- Continuous variables will be summarized with n, mean, standard deviation, median, minimum, and maximum.
- Categorical variables will be summarized by counts and by percentages of subjects in corresponding categories.
- All summary tables will be presented by treatment.
- Individual subject data obtained from the case report form (CRFs) and any derived data will be presented by subject in data listings. Data listings will be sorted by subject, and visit date and time, if applicable.

4.2. Adjustments for Covariates

There will be no adjustment for covariates.

4.3. Analysis Populations

4.3.1. *Intent-to-Treat Population*

An intent-to-treat (ITT) population will include subjects who received at least one intravenous injection and have post-injection efficacy measurements. This population will be evaluated for all efficacy variables.

4.3.2. *Per-Protocol Population*

All subjects valid for ITT who complete Visit 13 (Week 30) will be 'valid per protocol' (also called 'valid for efficacy'). Additional criteria may be added prior to unblinding the study database. As with the ITT population, this per-protocol (PP) cohort will also be evaluated for all efficacy variables.

4.3.3. *Safety Population*

A safety population will include subjects who received at least one intravenous injection and have post-injection safety measurements. This population will be evaluated for all safety variables.

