3.6.3 Safety Variables

- Hematology, blood chemistry and urinalysis at Visits 1, 3, 6, 9, 12, 13 and 14 or Early Termination. See Section Appendix 1 for a complete list of laboratory tests to be done.
- ECG evaluation at Visits 1, 3, 6, 9, 12, 13 and 14 or Early Termination
- Complete physical examination at Visits 1, 3, 6, 9, 12, 13 and 14 or Early Termination
- Vital signs (sitting blood pressure, pulse, breathing, and temperature) and weight will be measured at all visits.
- MRI Scan of the brain at Visit 1, 9, 13 and 14 or Early Termination.
- C-SSRS at Visit 3, 6, 9, 12, 13, and 14 or Early Termination
- Data regarding AEs and concomitant medications will be collected at all visits

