4.4. Baseline and Postbaseline Definition

Table 5 describes the rules for determining the patient population and baseline and postbaseline observations for study and type of analysis.

Table 5. Patient Population with Baseline and Postbaseline Definitions by Type of Analysis

Study Period/Analysis	Patient Population	Baseline Observation	Postbaseline Observation(s)
Treatment Period			
Primary Efficacy analyses	ITT Population with a baseline and at least 1 postbaseline observation	Visit 3	Visit 13
TEAEs	Safety Population	All Visits 1-3	All Visits 3.01-14
Serious Adverse Events, Discontinuations due to Adverse Events	Safety Population	N/A	
C-SSRS analyses	Patients with a baseline and at least 1 postbaseline C-SSRS assessment	All Prior History: Visits 1-3 including	All Visits 3.01-14
Treatment-emergent abnormal laboratory values	Safety Population with normal laboratory values at all nonmissing baseline visits (with respect to direction being analyzed) and who have at least 1 postbaseline observation	Low: Minimum from Visits 1-3 High: Maximum from Visits 1-3 Abnormal: All Visits 1-3	Low: Minimum from Visits 3.01-14 High: Maximum from Visits 3.01-14 Abnormal: All Visits 3.01-14
Treatment-emergent immunogenicity	Safety Population	Visit 3	All Visits 3.01-14
Treatment-emergent changes in temperature and weight	Safety Population with a baseline and at least 1 postbaseline observation	Low: Minimum from Visits 1-3 High: Maximum from Visits 1-3	Low: Minimum from Visits 3.01-14 High: Maximum from Visits 3.01-14
Treatment-emergent changes in blood pressures, pulse, and ECGs	Safety Population with a baseline and at least 1 postbaseline observation	Low: Last nonmissing from Visits 1-3 High: Last nonmissing from Visits 1-3	Low: Minimum from Visits 3.01-14 High: Maximum from Visits 3.01-14
Continuous safety analyses	Safety Population with a baseline and at least 1 postbaseline observation	Last of Visits 1-3	All scheduled visits 3 < Visits ≤ 14

ECGs = electrocardiograms; eCRF = electronic case report form; ITT = intent-to-treat; N/A = not applicable; TEAEs = treatment-emergent adverse events

Note: Visit 3.01 indicates the first unscheduled visit occurring after Visit 3 and prior to Visit 4.

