4.6. Treatment Group Comparability

4.6.1. *Patient Disposition*

Subject disposition information will be summarized for all subjects. Summaries will include: the number of subjects in each analysis population, the number of subjects completed the study, and the number of subjects discontinued study and its reason. All subjects randomized in the study will be included in the summary table. Patient allocation by investigator or site will be summarized. Patient allocation by investigator or site will also be listed as well.

4.6.2. *Protocol Deviations*

Listings of subjects with significant protocol deviations or violations will be provided. The following list of significant protocol violations will be determined from the clinical database and from the study clinical/medical group:

- Lack of informed consent or late informed consent
- Violations of inclusion/exclusion criteria
- Significant violations of prohibited concomitant medication usage as determined by the clinical/medical group
- Other significant protocol violations as determined by the clinical/medical group

4.6.3. *Patient Characteristics*

The following patient characteristics at baseline will be summarized by treatment group for all ITT patients:

- Demographic (age, gender, ethnic origin, height, weight, BMI)
- Medical history and Pre-existing condition

Medical history and pre-existing conditions will be summarized by preferred term (PT) within system organ class (SOC). Medical history is defined as illness(es) that ended prior to the signing of informed consent. Pre-existing conditions and AEs at baseline are those AEs occurring during the baseline/screening visits that is Visit 1, 2 and 3.

4.6.4. *Prior and Concomitant Therapy*

Verbatim terms on eCRFs will be mapped to Anatomical Therapeutic Chemical (ATC) class and Generic Drug Names using the World Health Organization (WHO) Drug Dictionary Enhanced (WHODDE) B2 format, March 1, 2015 release.

Prior medications are defined as medications started to take prior to the first injection. Concomitant medications are defined as medications started on or after the day of first injection of the study drug during the study.

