4.8. Safety Analyses

The safety and tolerability of treatment will be assessed by summarizing the following:

- AEs
- Treatment-emergent adverse events (TEAEs)
 - By PT
 - By SOC
 - By maximum severity
 - By considered to be related to investigational produce by investigator
- Serious Adverse Events (SAEs)
- AE leading to discontinuation
- Suicide-Related Thoughts and Behaviors
- Vital signs and weight
- Laboratory measurements
- Electrocardiograms (ECGs)

All safety analyses will be based on the safety population. AE rates will be summarized by treatment group and overall, and will be broken down by severity, seriousness and relation to study drug. Change of MRI, C-SSRS, physical examinations, vital signs, ECG

and standard laboratory results will be summarized with means, standard deviations, medians and ranges for continuous variables and with counts and percentages for categorical variables. Statistical tests are not planned for safety.

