4.8.1. Adverse Events

An AE is defined as any untoward medical occurrence in a subject who is administered a medicinal product and that does not necessarily have a causal relationship to the treatment. All AEs will be included in the data listings. Verbatim terms on case report forms will be mapped to preferred terms and system organ classes (SOC) using the Medical Dictionary for Regulatory Activities (MedDRA) (version 19.1).

A Treatment Emergent Adverse Event (TEAE) is defined as an adverse event that occurs on or after the treatment dose. TEAE summary will be displayed by treatment. Unless otherwise specified, summaries that are displayed by SOC and preferred terms will be ordered alphabetically by SOC, and within each SOC, preferred terms will also be ordered alphabetically. Summaries of the following types will be presented:

- Subject incidence of TEAEs by MedDRA SOC and preferred term.
- Subject incidence of TEAEs by MedDRA SOC, preferred term, and severity. Severity will be recorded as deemed by investigator. At each level of subject summarization, a subject is classified according to the highest severity if the subject reported one or more events.
- Subject incidence of study drug related TEAEs by MedDRA SOC and preferred term.
- Subject incidence of TEAEs by descending incidence of preferred terms.
- Subject incidence of serious TEAEs by MedDRA SOC and preferred term, if applicable.
- Subject incidence of TEAE leading to early termination by MedDRA SOC and preferred term, if applicable.

For each subject and for each adverse event, the duration of the event will be calculated as:

$$\text{Duration of AE} = \text{AE stop date} - \text{AE start date} + 1$$

The duration of AEs will be displayed in the data listing.

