4.10. Handling of Dropouts or Missing Data

No imputations will be made for missing values.

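### The Safety Population requires undefined post-injection data as well as an infusion, so an infused subject who is lost early may drop out of the adverse event denominators

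*SAP*

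**What the plan says.** The definition is identical in SAP 4.3.3 and Protocol 6.1.1.3: "A safety population will include subjects who received at least one intravenous injection and have post-injection safety measurements". The two conditions are joined by a conjunction, so an infusion alone does not qualify a subject. SAP 4.8 then states: "All safety analyses will be based on the safety population". Table 5 (SAP 4.4) assigns the set to the TEAE row and to the row for serious AEs and discontinuations due to AEs. The C-SSRS row has a set of its own, which also needs later data: "Patients with a baseline and at least 1 postbaseline C-SSRS assessment".

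Neither document defines a safety measurement. Protocol 3.6.3 includes this among the safety variables: "Data regarding AEs and concomitant medications will be collected at all visits".

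Two outputs do not depend on the set. For listings, SAP 4.8.1 says: "All AEs will be included in the data listings". For disposition, SAP 4.6.1 says: "All subjects randomized in the study will be included in the summary table". There is no fallback set of all infused subjects, and SAP 4.10 adds: "No imputations will be made for missing values".

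**The concern.** A safety set should be fixed by exposure. Here membership also depends on data obtained after exposure, so whether a subject is counted can depend on what happened to that subject after the infusion. Those most likely to lack later data are those who could not or would not come back, and the reason may itself be a safety outcome.

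The primary safety endpoint is a count of subjects with treatment-related AEs, and SAP 4.8 also reports AE rates by arm. With 11 per arm, each subject is 9.1% of the arm, so one exclusion shows in every AE table. Because the key term is undefined, two programmers could build different denominators and both claim to follow the SAP.

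**Working it through.** **1. Where the extra condition has any effect.** Reading Table 5 row by row:

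| Row | Set named | Own post-baseline requirement? |
|---|---|---|
| TEAEs | Safety Population | No |
| Serious AEs, discontinuations due to AEs | Safety Population | No |
| Immunogenicity | Safety Population | No |
| Abnormal laboratory values | Safety Population, restricted further | Yes |
| Temperature and weight | Safety Population, restricted further | Yes |
| Blood pressure, pulse, ECG | Safety Population, restricted further | Yes |
| Continuous safety | Safety Population, restricted further | Yes |
| C-SSRS | Own set | Yes |

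The condition is redundant in the measurement rows. It acts mainly on the event rows, where every exposed subject belongs in the denominator.

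**2. Can an infused subject have no qualifying data?**

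- Protocol 4.2.1 (Visit 3) lists vital signs, ECG, laboratory samples, AE recording and the infusion. It does not say that the items are in time order, and it names no measurement as post-infusion. It refers to Appendix 10.
- Appendix 10 plans observation during and after the infusion: site checks, questions about pain, signs of systemic infection, a note of the general response, and a stay of at least 1 hour.
- The next scheduled visit is Visit 4 at Week 2 (Protocol 4.2.2).
- Whether infusion-day findings are post-injection is unclear. SAP 4.6.3 says: "Pre-existing conditions and AEs at baseline are those AEs occurring during the baseline/screening visits that is Visit 1, 2 and 3". Table 5 starts the TEAE window at Visit 3.01, an unscheduled visit after Visit 3. SAP 4.8.1, however, counts events from the dose onward as treatment-emergent.
- Protocol 3.3 obliges a withdrawn subject to come back for early termination. Protocol 4.4 asks the site only to attempt to arrange that visit.

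Three readings follow:

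- (a) Infusion-day observation counts. The condition then excludes almost nobody.
- (b) Infusion-day observation does not count, but a recorded AE or death does. A subject lost with nothing recorded is excluded; a subject with an event stays in.
- (c) Only a value measured at a later visit counts. Both kinds of subject are excluded.

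**3. Size.** The plan has no figure of its own to reproduce. The planned n is 11 + 11 = 22, with no sample size calculation (Protocol 6.2, SAP 3.2).

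Reading (b), one event-free subject excluded from an arm of n = 11 with x events:

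- Ratio of percentages = [x/(n−1)] / [x/n] = n/(n−1) = 11/10 = 1.1.
- x = 1: 1/11 = 9.1% becomes 1/10 = 10.0%.
- x = 2: 2/11 = 18.2% becomes 2/10 = 20.0%.
- The count x does not change.

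Reading (c), excluded subjects with a related event. The exact (Clopper-Pearson) limits are the 0.025 quantile of Beta(x, n−x+1) and the 0.975 quantile of Beta(x+1, n−x), with lower limit 0 when x = 0:

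- One subject: 1/11 = 9.1% (0.2% to 41.3%) becomes 0/10 = 0% (0% to 30.8%). The last limit is 1 − 0.025^(1/10) = 0.308.
- Two subjects: 2/11 = 18.2% (2.3% to 51.8%) becomes 0/9 = 0% (0% to 33.6%).

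**4. How often.** The documents give no rate. As an assumption, let each infused subject have probability p of no qualifying data. The chance of at least one exclusion among 22 is 1 − (1−p)^22: about 20% for p = 1%, 36% for 2%, 68% for 5% and 90% for 10%.

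**The case against.** The strongest reply is that the exclusion will rarely occur. Appendix 10 has every infused subject watched on the day. AE data are safety variables (Protocol 3.6.3), AEs after the first dose go into the eCRF (7.2), death is a serious AE outcome (7.1.2), and serious AEs are reportable from the first administration (7.3). On an ordinary reading, a recorded AE or death is post-injection safety data and keeps the subject in the set. A subject lost with nothing recorded adds nothing to the event count under either definition. No safety tests are planned (SAP 4.8), and listings and disposition would show the case.

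Most of this stands, and it rules out several stronger inferences:

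- A reader might infer that nothing is observed between the first infusion and Week 2. Appendix 10 contradicts that.
- A reader might infer that a subject who dies after infusion is removed from all safety tables. The text requires that only on reading (c), which is the least natural one.
- A reader might infer that such a subject disappears from the report, or that oversight is weakened. The listings and disposition table remain, and the two-death criterion in Protocol 3.4 is not tied to this set.
- A reader might infer that a partial infusion is excluded. The documents are silent on this.

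The reply does not remove the ambiguity. No passage says that Appendix 10 observation or an AE entry is a safety measurement, and the treatment of Visit 3 AEs as baseline points partly the other way.

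**Conclusion.** The concern holds in limited form. The set is conditioned on post-exposure data of an undefined kind, and an infused subject who withdraws or is lost before any later visit may be left out of the TEAE, serious AE and AE-discontinuation summaries.

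The firmer consequence is a denominator of 10 instead of 11, which multiplies that arm's AE percentages by 1.1 and leaves the count of subjects with related events unchanged. It assumes that infusion-day observation does not count. The change from 1/11 to 0/10 needs the further assumption that a recorded event does not count either, and should be cited only with that condition. How likely any exclusion is cannot be judged from the documents. The change is worth making because the condition contributes almost nothing where it is harmless and can only distort the event tables.

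**What to change.** In SAP 4.3.3 and Protocol 6.1.1.3, delete the condition on post-injection safety measurements. Define the Safety Population as all subjects in whom any study infusion was started, analysed by product received. This also settles how a stopped infusion is counted.

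The laboratory, temperature and weight, blood pressure, pulse and ECG, and continuous rows of Table 5 already carry their own post-baseline requirement and need no edit. If the immunogenicity row is meant to need a later sample, add that phrase to the row.

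The cost is one sentence in each document. It needs no new data and changes no procedure. Make the change before the database is unblinded. If only the SAP is changed, SAP section 5, which says that no departures from the protocol's analyses are planned, must record it.
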